9. STUDY POPULATION

The study population will be described by the parameters below. Listings and summaries will be based on the Randomized Population unless otherwise noted.

9.1 Study Participant Disposition

Frequencies and percentages of Study Participants who discontinued the study treatment and/or study will be summarized. Reasons for discontinuation will also be summarized. The listing of Study Participant disposition will include dates and times (if applicable) of randomization, dosing, and EOS; and reasons for study treatment and/or study discontinuation (if applicable). Reasons for screen failure will be summarized separately.

9.2 Eligibility and Informed Consent

Eligibility and informed consent parameters will include protocol version (all subjects were enrolled under Final, 10 Jul 2018, Administrative Change Number 1.0 Version 1.0, 15Nov2018), date of informed consent, and inclusion criteria met or exclusion criteria not met. Satisfaction of

Confidential Page 14 of 33

inclusion/exclusion criteria will be summarized. Screen failures will be listed and summarized separately; the summary will include broad reason for screen failure.

9.3 Protocol Deviations

In addition to the listing of eligibility detailed in Section 9.2, a separate listing will show all other protocol deviations and will include protocol version and the category of the deviation (to be determined). Frequency and percentage of subjects in each deviation category will be summarized.

9.4 Analysis Populations

The analysis populations defined in Section 7 will be described in terms of the identification of Study Participants in each population and the frequency distribution of each population. Number of screened Study Participants will be the denominator for percentage of randomized Study Participants, and number of randomized Study Participants will be the denominator for percentage of Study Participants in the Safety Population.

A listing of analysis populations will be produced using the Randomized Population only and will show the analysis population(s) to which each Study Participant belonged.

9.5 Demographic and Baseline Characteristics

Demographic and other baseline characteristics will be summarized, both overall and by treatment group, for the Safety Population. Parameters will include study site, sex, age at informed consent, race, ethnicity, fertility status (women only), and measurements of weight and height, and body mass index (BMI) at screening.

9.6 Medical History

Reported medical conditions will be coded using the Medical Dictionary for Regulatory Activities (MedDRA), version 21.1 or later, to a System Organ Class (SOC) and Preferred Term (PT). Medical history, including SOCs and PTs, will be listed but not summarized. A separate listing will detail prior experience using an intranasal device.

9.7 Physical Examination

Physical examination findings for each body system will be summarized. Of note, abnormal findings are to be recorded in the eCRF as medical history.

9.8 Urine Pregnancy Test

Results from the urine pregnancy test will be listed but not summarized and will be limited to female Study Participants. If a female Study Participant is not of childbearing potential, this will be indicated in the listing in place of the test result.

10. TREATMENTS

Treatments include study treatment, prior medications, and concomitant medications.

Confidential Page 15 of 33

10.1.1 Study Treatment Exposure

Total exposure will be expressed as number of sprays and will be summarized both per nostril and overall. Listings and summaries will be based on the Safety Population.

10.1.2 Prior and Concomitant Medications

Medication use from 2 weeks prior to screening to EOS will be coded to generic terms, including 2nd-level Anatomical-Therapeutic-Chemical (ATC) drug class, using the World Health Organization Drug Dictionary (WHO-DD), version September 2018 or later. Aside from parameters collected on the eCRF, listings will include date and time of study treatment dosing, WHO-DD drug class and preferred drug name, and Study Day. Frequencies and percentages of subjects reporting or receiving each medication will be summarized by WHO-DD drug class and preferred name within drug class.

Medications that were stopped prior to study treatment dosing will be considered "prior" medications," medications that were stopped earlier than 2 weeks before screening will be ignored, and all other medications will be considered "concomitant." Medications recorded with insufficient exposure dates to determine whether or not they were concomitant will be considered concomitant.

Prior medications will be listed and summarized separately from concomitant medications. Listings and summaries for prior medications will be based on the Randomized Population. Listings and summaries for concomitant medications will be based on the Safety Population.

11. SAFETY PARAMETERS

Safety parameters will be listed for the Randomized Population and summarized for the Safety Population unless otherwise noted.

11.1 **AEs**

AEs reported from time of first dose through EOS will be coded according to MedDRA® version 21.1 or later. Each reported AE will be mapped to a PT and SOC. Aside from parameters collected on the eCRF, listings will include date and time of study treatment dosing, MedDRA PT and SOC, Study Day, whether or not the AE is ongoing, AE duration, and whether or not the AE resulted in study discontinuation. For AEs that are ongoing, AE end date will be imputed with subject-level EOS date for the duration calculation.

A treatment-emergent AE (TEAE) will be defined as an AE that began or worsened during or after study treatment dosing on Day 1 and no later than on Day 2. AEs with insufficient date or time information to determine whether or not they were treatment-emergent will be considered treatment-emergent. AEs that began or worsened in severity from Day 3 through EOS will be defined as non-treatment-emergent. AEs that began or worsened in severity before first dose will be recorded as medical history.

All TEAEs will be listed. In addition, separate listings will be done for:

- Treatment-emergent SAEs (TESAEs), to include seriousness criteria
- TEAEs that resulted in study treatment interruption or dose reduction

Confidential Page 16 of 33

- TEAEs that results in discontinuation from the study or study treatment (excluding deaths)
- TEAEs that resulted in death
- Non-treatment-emergent AEs

Listings will be done for the Safety Population.

Incidence of all TEAEs will be summarized by SOC and PTs within SOCs, sorted alphabetically by SOC and PT within SOC unless otherwise noted. In addition, separate summaries will be done for:

- TEAEs assessed as related to study treatment
- TEAEs by maximum severity, with both SOCs and PTs within SOCs sorted by descending incidence among all Study Participants combined
- TESAEs
- TESAEs assessed as related to study treatment

In summaries by relationship to study treatment and maximum severity, missing relationship will be considered related and missing severity will be considered severe. Only the most related TEAE per subject for a given PT will be counted in summaries by relationship; similarly, only the most severe TEAE will be counted in summaries by severity.

An overall summary of TEAEs (collapsed over all SOCs and PTs) will show incidence of all TEAEs as well as:

- TEAEs assessed as related to study treatment
- TESAEs
- TESAEs assessed as related to study treatment
- Severe TEAEs
- Moderate TEAEs
- TEAEs that resulted in death
- TEAEs that resulted in study treatment interruption or dose reduction
- TEAEs that results in discontinuation from the study or study treatment (excluding deaths)

Summaries of TEAEs and TESEAs (separately) in descending order of incidence among all Study Participants combined will show incidence of PTs only.

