4 ADVERSE EVENT REPORTING

Throughout the course of the study, all AEs will be monitored and recorded on an AE eCRF, including the AE's description, start and end date, seriousness, severity, action taken, and relationship to the study drug. If AEs occur, the first concern will be the safety of the subjects. All AEs will be followed until resolved or stable and the outcome documented on the eCRF.

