4.1 Definitions and Criteria

4.1.1 Adverse Events

Per ICH E2A²⁹: An AE is any untoward medical occurrence in a patient or clinical investigation subject administered a pharmaceutical product and which does not necessarily have to have a causal relationship with this treatment. An AE can therefore be any unfavorable and unintended sign (including an abnormal laboratory finding, for example), symptom, or disease temporally associated with the use of a medicinal product, whether or not considered related to the medicinal product.

Medical interventions such as surgeries, diagnostic procedures, and therapeutic procedures are not AEs but the action taken to treat the medical condition. They should be recorded as treatment of the AEs.

Any AE that has an onset on or after the dose of study drug, or any pre-existing condition that has worsened on or after the first dose of study drug will be considered a treatment-emergent adverse event (TEAE).

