4.1.4 Assessing Intensity and Relationship

All AEs will be assessed on 2 descriptive parameters: intensity and relationship to the study drug:

- Intensity refers to the severity of an event and references impact on a subject's functioning.
- Relationship refers to the likelihood that the event being assessed was caused by the study drug.

Intensity

Each AE will be classified according to the following criteria:

Mild:	The AE does not interfere in a significant manner with the subject's normal level of functioning.
Moderate:	The AE produces some impairment of functioning, but is not hazardous to the subject's health.
Severe:	The AE produces significant impairment of functioning or incapacitation and is a definite hazard to the subject's health.

When changes in the intensity of an AE occur more frequently than once a day, the maximum intensity for the experience should be noted. If the intensity category changes over a number of days, those changes should be recorded separately (with distinct onset dates).

Relationship

The investigator must assess the causality of an AE (including SAEs) to the use of a study drug using a 2-category scale (not related or related) based on clinical judgment and using all available information, and may include consideration of the following factors:

- Possible alternative causes of the AE, including the disease under treatment, pre-existing conditions, concomitant use of other drugs, and presence of environmental or genetic factors
- The temporal association between study drug exposure and onset of the AE
- Whether the manifestations of the AE are consistent with known actions or toxicity of the study drug
- Whether the AE resolved or improved with stopping use of the study drug; judgment should be used if multiple products are discontinued at the same time
- Positive rechallenge
- Positive dechallenge (resolution upon stopping suspect study drug, in absence of other intervention or treatment)

The causal relationship between the study drug and the AE will be assessed using one of the following categories shown in Table 4.1:

Table 4.1: Adverse Event Causality

Category	Definition
Not Related	An AE is not associated with study medication if no causal relationship exists between the study drug and the AE, but an obvious alternative cause exists, eg, the subject's underlying medical condition or concomitant therapy.

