5.2.7.2 Adverse Events

AEs will be coded in accordance with the latest version of the Medical Dictionary for Regulatory Activities (MedDRA). Incidence for all reported AEs will be summarised overall (regardless of severity or relationship to study drug), moderate AEs, and severe AEs. Additionally, a summary

of SAEs and AEs leading to early termination from the study will be presented along with corresponding data listings.

The incidence of TEAEs will be summarised as the number and percentage of subjects and events reported by treatment and overall for each System Organ Class and Preferred Term using the Safety Analysis Population. TEAEs will also be summarised by maximum severity and relationship to study drug.

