4.2 Study Endpoints

4.2.1 Primary Endpoints

Primary endpoints are related to safety:

- Incidence, seriousness, severity, and relatedness to study treatment of adverse events (AEs) recorded over 60 minutes post dose and at Day 7
- Change from Baseline in vital signs (oral temperature, respiratory rate, pulse, blood pressure) at 60 minutes post dose
- Change from Baseline in ear, nose, and throat (ENT) examination (otoscopy of the ear, nose, and oropharynx) findings at 60 minutes post dose
- Change from Baseline in the appearance of the tympanic membrane (TM) (contour, color, fluid, translucency) as measured by otoscopy at 60 minutes post dose

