| 14.3.1.3.3 | TESAEs by PT in Descending Order of Incidence | Safety | | |
| 14.3.1.4 | Non-Treatment-Emergent Adverse Events | Safety | | |

Confidential Page 30 of 33

| 14.3.6 | Concomitant Medications | Safety |
|----------|---|--------|
| 14.3.7.1 | ENT Examination, Observed Values | Safety |
| 14.3.7.2 | ENT Examination, Shifts from Baseline | Safety |
| 14.3.8.1 | Otoscopy, Observed Values | Safety |
| 14.3.8.2 | Otoscopy, Shifts from Baseline | Safety |
| 14.3.9.1 | Vital Signs, Observed Values and Changes from Baseline | Safety |
| 14.3.9.2 | Vital Signs, Incidence of Clinically Meaningful Changes from Baseline | Safety |

Confidential Page 31 of 33

FIGURES

| NUMBER | TITLE | POPULATION |
|-------------|---|------------|
| Exploratory | / Endpoints | |
| 14.2.1.1.1 | VAS Least-Squares Mean (SE) Change from Baseline (PID) | Safety |
| 14.2.1.1.2 | NRS-11 Least-Squares Mean (SE) Change from Baseline (PID) | Safety |
| 14.2.1.2.1 | VAS Least-Squares Mean (SE) SPID | Safety |
| 14.2.1.2.2 | NRS-11 Least-Squares Mean (SE) SPID | Safety |
| 14.2.1.3.1 | VAS Response, 25% | Safety |
| 14.2.1.3.2 | VAS Response, 50% | Safety |
| 14.2.1.3.1 | VAS Response, 75% | Safety |
| 14.2.1.4.1 | NRS-11 Response, 25% | Safety |
| 14.2.1.4.2 | NRS-11 Response, 50% | Safety |
| 14.2.1.4.3 | NRS-11 Response, 75% | Safety |
| 14.2.2.1.1 | PGIC Least-Squares Mean (SE) Change from Baseline | Safety |
| 14.2.2.1.2 | PGIC Response | Safety |
| 14.2.2.2.1 | CGI-I Least-Squares Mean (SE) Change from Baseline | Safety |
| 14.2.2.2.2 | CGI-I Response | Safety |

Confidential Page 32 of 33

LISTINGS

| NUMBER | TITLE | POPULATION | | |
|------------------------|---|--------------------------------|--|--|
| Study Population | | | | |
| 16.2.1 | Study Participant Disposition | Randomized | | |
| 16.2.2.1 | Eligibility and Informed Consent | Randomized | | |
| 16.2.2.2 | Reasons for Screen Failure | Screening excluding Randomized | | |
| 16.2.2.3 | Protocol Deviations | Randomized | | |
| 16.2.3 | Analysis Populations | Randomized | | |
| 16.2.4.1 | Demographic and Baseline Characteristics | Randomized | | |
| 16.2.4.2.1 | Medical History | Randomized | | |
| 16.2.4.2.2 | Prior History Using an Intranasal Device | Randomized | | |
| 16.2.4.3.1 | Physical Examination | Randomized | | |
| 16.2.4.3.2 | Urine Pregnancy Test | Randomized excluding males | | |
| 16.2.4.5 | Prior Medications | Randomized | | |
| 16.2.5 | Study Treatment Exposure | Safety | | |

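### The SAP closes the treatment-emergent window on Day 2, so every planned severity, relatedness and SAE table leaves out AEs starting on Days 3-7, although the primary endpoint runs to Day 7

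*SAP*

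**What the plan says.** SAP 11.1 limits a TEAE to an AE that "began or worsened during or after study treatment dosing on Day 1 and no later than on Day 2". It then adds: "AEs that began or worsened in severity from Day 3 through EOS will be defined as non-treatment-emergent". AEs whose dates are too incomplete to classify default to treatment-emergent.

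The SAP's primary AE endpoint (4.2.1) is "Incidence, seriousness, severity, and relatedness to study treatment of adverse events (AEs) recorded over 60 minutes post dose and at Day 7".

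Protocol 4.1.1 defines a TEAE without an end day: "Any AE that has an onset on or after the dose of study drug", or a pre-existing condition that worsens from dosing onward. Protocol 3.5.5 collects AEs until the follow-up call or early termination. Protocol 5.2.7.2 plans: "Incidence for all reported AEs will be summarised overall (regardless of severity or relationship to study drug), moderate AEs, and severe AEs". It adds a summary of SAEs and of AEs leading to early termination, and summaries of TEAEs by maximum severity and by relationship.

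In SAP 11.1 and Appendix B, the overall summary (with its severe, moderate, related, serious, death and discontinuation rows) and all tables by severity, relatedness or seriousness use TEAEs or TESAEs only. Later AEs go to Table 14.3.1.4, titled "Non-Treatment-Emergent Adverse Events", and to Listing 16.2.7.2.

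The AE endpoint row in SAP Section 15 (changes from the protocol) keeps Day 7. No row mentions the Day 2 cut.

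**The concern.** The tables that should deliver the primary endpoint do not cover its time span. If SAP 11.1 is followed exactly, a drug-related, severe or serious AE that starts on Day 4 enters none of the specified relatedness, severity or SAE summaries. It is also absent from the listings of serious and fatal events (14.3.2.1 and 14.3.2.4). The report could state that there were no treatment-emergent SAEs and be correct under the SAP, although an SAE had occurred within planned follow-up and met the protocol's TEAE definition.

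The two SAP definitions also overlap. An AE that begins on Day 1 and worsens on Day 4 satisfies both. Protocol 4.1.4 instructs: "If the intensity category changes over a number of days, those changes should be recorded separately (with distinct onset dates". If the later, more severe record is classified by its own date, an AE that progressed from mild to severe can appear as mild in the maximum-severity table. The SAP gives no rule for this case.

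The stakes are high for this study. Safety is its only primary objective, and the protocol says OP0201 has had no prior clinical studies in humans (1.1.2) and that its risks are unknown (1.5).

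**Working it through.** The plan states no figure for this point, so there is none to reproduce. The check compares the definitions, counts the outputs and illustrates the size.

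**1. Windows side by side**

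| Source | Time span for AEs |
|---|---|
| SAP 4.2.1, primary endpoint | Recorded over 60 min and at Day 7 |
| SAP 11.1, TEAE | Dosing to Day 2 |
| SAP 11.1, non-treatment-emergent | Day 3 to end of study |
| Protocol 4.1.1, TEAE | From dosing, no end day |
| Protocol 3.5.5, AE collection | From dosing to follow-up call or early termination |

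SAP 8.6 makes the dosing day Day 1. The TEAE window is therefore Days 1-2, and Days 3-7 fall outside it: 5 of 7 study days, 5/7 = 71%. This is a share of days, not of AEs. Under the same formula, a call exactly one week after dosing falls on Day 7 + 1 = 8, which would make the omitted span 6 days.

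**2. Outputs in SAP Appendix B**

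- Tables restricted to TEAEs or TESAEs: 14.3.1.1, 14.3.1.2.1 to 14.3.1.2.4 (four), and 14.3.1.3.1 to 14.3.1.3.3 (three). That is 1 + 4 + 3 = 8. Only 14.3.1.4 covers later AEs, so 8 of 9 are restricted.
- Listings restricted to TEAEs or TESAEs: 16.2.7.1 and 14.3.2.1 to 14.3.2.4. That is 1 + 4 = 5. Only 16.2.7.2 covers later AEs, so 5 of 6 are restricted.

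Listing 16.2.7.2 carries the eCRF fields, which under protocol Section 4 include "start and end date, seriousness, severity, action taken, and relationship to the study drug". The attributes of late AEs are therefore recorded and listed. What is missing is a specified summary of them by arm.

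**3. Effect of one subject on one row**

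Planned arm size is 12 (protocol 5.2.1). Take a subject with no Day 1-2 event in that row and one event on Days 3-7. Exact (Clopper-Pearson) 95% limits show how coarse the scale is; the SAP plans no such intervals for AEs.

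- Day 2 cut: 0/12 = 0%. Upper limit 1 − 0.025^(1/12) = 26.5%.
- Window to end of study: 1/12 = 8.3%, limits 0.2% to 38.5%.

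**4. Chance that the gap matters at all**

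The documents give no risk of an AE starting on Days 3-7, so the per-subject risk *p* is an assumption. P(at least one among 24) = 1 − (1 − p)^24.

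| Assumed p | P(at least one in 24) |
|---|---|
| 1% | 21% |
| 2% | 38% |
| 5% | 71% |
| 10% | 92% |

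These figures are for any AE. Related, severe or serious AEs would have smaller risks, on which the documents are silent.

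**The case against.** The strongest reply has five parts.

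- **Recording, not onset.** SAP 4.2.1 says when AEs are recorded; it does not set an onset window. That is a fair reading of the words. But an AE that starts on Day 4 and is reported at the Day 7 call is recorded at Day 7, so the endpoint includes it, and its severity and relatedness still go unsummarised.
- **Precedence.** Protocol 5.2 lets the SAP's analyses supersede the protocol's. This weakens the conflict with protocol 4.1.1 and 5.2.7.2. It does not settle a conflict between two sections of the SAP. The same protocol section says deviations will be set out in the SAP, yet Section 15 records changes as small as listing order and omits this one.
- **Late AEs remain visible.** They appear in Table 14.3.1.4 and Listing 16.2.7.2. A death, or an AE that ends participation, would also appear among the reasons for discontinuation, and expedited SAE reporting does not depend on the label. All of this stands, and with about 24 subjects a line listing can be read in full. None of it gives severity, relatedness and seriousness by arm, which is the endpoint.
- **Titles only.** Appendix B shows no table layouts, so Table 14.3.1.4 might include the breakdowns. True, but none is specified.
- **Size and the worsening example.** The 21% to 92% range covers any AE, including mild unrelated ones, and the output count includes tables that re-sort the same events. The mild-to-severe example depends on how the separate record is classified. These points limit what the figures show; they do not remove the defect.

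**Conclusion.** The concern holds and must be fixed. As written, SAP 11.1 keeps AEs known to start on Days 3-7 out of every specified severity, relatedness and SAE summary, while SAP 4.2.1 makes those attributes a primary endpoint up to Day 7. This is a conflict in the stated rules, not missing detail, and Section 15 does not disclose it.

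The structural size is certain: 8 of 9 AE tables, 5 of 6 AE listings and 5 of 7 study days, taking the call on Day 7. The number of AEs affected is unknown. The probabilities rest on assumed risks of any AE and show only that an affected event is plausible in 24 subjects. The data are not lost, so the harm is to the summaries and to the statements drawn from them.

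**What to change.** In SAP 11.1, define a TEAE as an AE that begins or worsens at or after dosing, through at least the follow-up call or end of study, in line with protocol 4.1.1. Tie the window to the call or end of study so that a call falling on Day 8 is covered. Run the 14.3.1.x tables and the 14.3.2.x listings on that definition. Onset by Day 2 can be an optional subset.

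State how an AE that worsens after onset, and is recorded separately under protocol 4.1.4, enters the maximum-severity table.

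Table 14.3.1.4 and Listing 16.2.7.2 would then hold only events outside the window, such as those reported after the call. SAP 11.1 at present codes AEs only to end of study, so using them this way needs a coding rule for such events.

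If the Day 2 cut is kept instead, make the two categories mutually exclusive, tabulate Day 3 to end-of-study AEs by arm with the same severity, relatedness and seriousness breakdowns, and record and justify the change in Section 15.

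The cost is SAP wording and minor programming; no new data are needed. Counts in the TEAE tables may look slightly less favourable.
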